3.2.2 Cardiovascular Use case

Objective. The objective of the endpoints below is to demonstrate the value of having interoperable and reusable data in a standard format to generate valuable and high-quality information in clinical care, without additional burden to the treating physicians.

Objective	(Secondary) end point
Metric 1. Compare scoring time	Metric definition: Time to compute the SMART score (see
between AIDAVA and CVD	definition below)
expert	
	Measurement:

Objective	(Secondary) end point	
	TCVD. Time required for the treating physician to compute the SMART risk score (collect + analyse + enter data into a standalone web page calculator) - per estimate of user in dedicated entry form - compared to the time needed to calculate the same score by AIDAVA, automatically (G1 and G2)	
Metric 2: Compare scoring accuracy between AIDAVA and CVD expert	Metric definition: Accuracy of automatic calculation of the U-Prevent SMART risk score compared to cardiovascular expert-entered score calculation (% difference in the score output - per estimate of user in dedicated entry form) (G1 and G2)	
	 Measurement: CVD1. U-Prevent SMART score computed by treating physician (https://u-prevent.com/calculators/smartScore) CVD2. U-Prevent SMART score computed by AIDAVA 	

The SMART Risk Score [4] is a tool to estimate 10-year risk for recurrent vascular events in patients with manifest cardiovascular disease. The calculator is located at the U-Prevent site [5], a clinical decision support platform, for the application of risk prediction models in clinical practice; the calculator has been recreated and optimised by ORTEC for personalised cardiovascular risk management. The U-Prevent site is CE marked according to the Medical Devices Directives (MDD); marking for MDR compliance is in progress. The pilot site was built by UMC Utrecht. Using the calculators is free. The U-Prevent team develops extra services for premium users, optimization of data management, e.g. by FAIR and GDPR-compliant data exchange from electronic health records. Technical specification to compute Model A, the SMART Risk Score [6] can be found below.

Formulas	SNOMED / LOINC Code (available in PHKG)	Population ¹² value if missing
Recalibrated SMART risk score for	patients with CVD:	
10-year cardiovascular disease risk	: (%) = (1- 0.71840 exp[A + 1.933]) x 100%	
where A =		
-0.0349602236 x age in years	Compute from SNOMED: 184099003 Date of birth	Mandatory

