+ 0.0005510715 x (age in	(observable entity)	
years)²		
+ 0.2876587433 [if male]	Answer is Y in case of presence of	Mandatory
	SNOMED: 248153007 Male (finding)	
+ 0.3455832714 [if current	A= last occurrence of smoker SNOMED: <<	Mandatory
smoker]	77176002 Smoker (finding)	(default = N)
	B = last occurrence of	
	Quit-Smoking (<< 160617001 Stopped smoking)	
	OR Ex-Smoker (<< 8392000 Non-smoker)	
	IF time of A is after B,	

¹² Numbers from Dutch population (baseline characteristics from the SMART study); it is valid for male/female and all ages. The same number can be used across the EU population.

Formulas	SNOMED / LOINC Code (available in PHKG)	Population ¹² value if missing
	THEN value is Y FLSE value is N	
+ 0.0018913154 * systolic blood pressure in mmHg	Take last value in PHKG ; SBP= LOINC: 8480-6	Mandatory
	(average value across a period of time)	
+ 0.3181706587 [if diabetic]	Answer is Y in case of presence of SNOMED: << 73211009 Diabetes mellitus (disorder) (and all children codes)	VAL = 17% * 0.223 (average)
+ 0.2947019539 [if history of coronary artery disease, of acute coronary syndrome, myocardial infarction or coronary revascularization]	 Answer is Y in case of presence of SNOMED: << 53741008 Coronary arteriosclerosis (disorder) (and all children codes) OR SNOMED: << 394659003 Acute coronary syndrome (disorder) (and all children codes) OR SNOMED: << 22298006 Myocardial infarction (disorder) (and all children codes) OR SNOMED: << 415070008 Percutaneous coronary intervention (procedure)>> (and all children codes) OR SNOMED: <<232717009 Coronary artery bypass grafting (procedure) >> (and all children codes) 	Mandatory (default = N)
+ 0.3483178604 [if history of cerebrovascular disease, TIA, brain infarction, amaurosis fugax, retina infarction or carotic surgery]	 Answer is Y in case of presence of SNOMED: << 230690007 Cerebrovascular accident (disorder) (and all children codes) OR SNOMED: << 266257000 Transient ischemic attack (disorder) (and all children codes) OR SNOMED: << 432504007 Cerebral infarction (disorder) (and all children codes) OR SNOMED: << 88032003 Amaurosis fugax (disorder) (and all children codes) OR SNOMED: << 175362007 Carotid and/or cerebral and/or subclavian artery operations (procedure) (and all children codes) 	Mandatory (default = N)

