+ 0.0396752081 * eGFR ² (in mL/min/1.73m ² + 0.0002186126 * eGFR ² (in mL/min/1.73m ²) + 0.1517601731 * log(High	Last value LOINC: 62238-1 If not available, derive from creat(SerumCreatine in micromol/l (LOINC = LP145994-2) (per paper Based on Heart. 2013 Jun;99(12):866-72 & Circulation. 2016 Nov 8;134(19):1419-1429 eGFR in mL/min per 1.73 m2 = If patient is male (SNOMED: 248153007) THEN = 32788 * creat ^(-1.154) * age ^(-0.203) ELSE 32788 * creat ^(-1.154) * age ^(-0.203) * 0.742 If the last value of LOINC: 30522-7 is above 15 then	VAL creatine = 92 micromol/l (to be transformed) VAL = 2.2mg/l =
Sensitivity-CRP in mg/dL)	use the previous value (up to the time the value is below 15). If there is no value below 15, then take default	22mg/dL

Formulas	SNOMED / LOINC Code (available in PHKG)	Population ¹² value if missing
+ 0.2107210313 * usingAnticoag	 Answer is Y in case of presence of one or more drugs of category Platelet aggregation inhibitors excl. Heparin (ATC = B01AC) OR A combination of One or more drugs of category Platelet aggregation inhibitors excl. Heparin (ATC = B01AC) + one or more drug of category Direct factor Xa inhibitors (ATC = B01AF) 	VAL = Y
	 Example: can be Ascal, aspirin or an other equivalent (AAS, carbasalate calcium) Dual antiplatelet therapy : Ascal / aspirin + a P2Y12 inhibitor Direct oral anticoagulants (DOAC) P2Y12 inhibitor Ascal / Aspirin + low dose direct working oral anticoagulation (DOAC) 	

In case of missing data, some parameters can use population average value as indicated in the last column. If a mandatory value is missing, the default value indicated in the last column will be used. Note: it is expected that birthdate, gender and systolic blood pressure will be available. The score will be computed by AIDAVA and by the treating (junior) physician. It will then be checked by the senior physician; in case of discrepancy between the score computed by AIDAVA and by the physicians, the senior physician will require explanations on how AIDAVA came to the different answers/codes needed to compute the score and decide the reason for discrepancy.

The senior physicians will be presented with a table with all the parameters used to compute the score (as displayed in the figure below) and be able to get information on how AIDAVA came to a certain value (which data source, which transformation).

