G1 and G2 VISIT 1 - on site W1 Day 1 (either elective outpatient clinic visit OR inpatient stay during index MI event),	 Approximately up to 50 inpatients screened, 15 inpatients enrolled (Note: Day1 and Day2 may seem busy for a patient recovering from MI; most patients are however recovering well and find difficult to remain in hospital during the monitoring period) 1. Checking I/E criteria (In REDcap) 2. Project introduction (10 min, doctor). Research associate complete REDCap Form (in REDCap, Patient Screening FORM) If the patient meets the criteria and is interested in participating in the project, he/she will move on to the research associate 3. Under supervision of Research Associate - 30-60 min per patient 	

	CVD patients	BC patients
	 a. Share details of the project with patients ; b. Provision of SIP and explanation - including use of EQ-5D QALY - quality of life questionnaire several time c. Introduction of HDI and questions regarding ownership and future use of the data through HDI d. Answer to questions e. Request to read and sign ICF and HDI agreement f. Provide medical device to patient 4. Research associate update REDCap Form (in REDCap, Patient Screening FORM) 5. Confirmation of patient enrollment; 	
	 Create HDI account (through AIDAVA) Questionnaire to specify user profile (In REDCap 3. Training session for the patient on the prototyp Patient fills EQ-5D form through HDI provided a Research associate complete REDCap Form (sources for enrolled patients Patient and expert curator curate medical data), User Profile FORM) e by the research associate pp in REDCap, Patient monitoring FORM) data extraction from different with AIDAVA
W1	CVD patient will use medical device	
Day 2 - 5	 Patient will use AIDAVA and test its functionalities, take notes and if necessary, will contact Helpdesk whenever needed Expert curator will curate the data in AIDAVA on demand. RA fill the patient monitoring form (in REDCap, Patient monitoring FORM) 	
W1 Day 5	 First calculation of SMART risk score by AIDAVA (automatically) and CVD expert (manually). Data collection and entry forms : Documentation of SMART risk score calculation result and time (in REDcap, Patient Monitoring FORM) by RA 	 System extracts the patient data for insertion into the local AIDAVA BC registry Queries identified as secondary end points will be fired automatically by the system and results available for display to the BC data users

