10.6. SMART risk score

#Last update: 27 - 01 - 2022

smart2 <- function(age, sex, isSmoking, sbp, diabetesDiagnosis, coronaryArteryDisease, cerebrovascularDisease, peripheralArteryDisease, aorticAneurysm, yearsSinceFirstDiagnosis, hdlCholesterol, totalCholesterol, creatinin, crp, hrFutureEvent = 1, usingAnticoag, region){

LP <- NULL tenYearRisk <- NULL

sex <- ifelse(sex==1, "M", "F")</pre>

#Berekenen eGFR obv CKDepi
gfr <- ifelse(sex=="M", 32788*creatinin^(-1.154)*age^(-0.203),
32788*creatinin^(-1.154)*age^(-0.203)*0.742)</pre>

#Berekenen non-HDL obv totaal cholesterol en HDL nonHdl <- totalCholesterol - hdlCholesterol

LP= -0.0349602236 * age + 0.0005510715 * age^2 + ifelse(sex=="M", 0.2876587433, 0) + 0.3455832714 * isSmoking + 0.0018913154 * sbp + 0.3181706587 * diabetesDiagnosis + 0.2947019539 * coronaryArteryDisease + 0.3483178604 * cerebrovascularDisease + 0.3303566308 * aorticAneurysm +

¹⁸ As defined in European Risk Regions (heartscore.org) -Netherland: Low; Austria: moderate; Estonia: High

0.2244665798 * peripheralArteryDisease + 0.0476995851 * yearsSinceFirstDiagnosis -0.0016497342 * yearsSinceFirstDiagnosis^2 + 0.5403642493 * log(nonHdl) -0.0396752081 * gfr + 0.0002186126 * gfr^2 + 0.1517601731 * log(crp) -0.2107210313 * usingAnticoag

tenYearRisk <- 1 - (1-0.1658228)^exp(LP + 0.0463729 - log(ratioRegion)) tenYearRisk <- ifelse(tenYearRisk==1,0.9999999,tenYearRisk)

tenYearRiskWithTreatment <- 1 - (1-tenYearRisk)^(hrFutureEvent) #hrFutureEvent komt uit behandeleffectenscript

return(

) }

```
list(
currentTenYearRisk = tenYearRisk,
tenYearRiskWithTreatment = tenYearRiskWithTreatment
)
```

11. Regulatory, Ethical, and Study Oversight Considerations

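### AIDAVA's SMART score follows input-selection rules that the physician's reference score is not required to follow, so correct extraction can count as inaccuracy, chiefly through CRP

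*Protocol*

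**What the plan says.** The SMART table in Section 3.2.2 maps each term of the score to codes in the patient's knowledge graph and states which recorded value to use. Three rows matter here.

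- **CRP.** If the last value exceeds 15 (no unit given), AIDAVA is to "use the previous value (up to the time the value is below 15). If there is no value below 15, then take default". The default is 2.2 mg/L.
- **eGFR.** "Last value LOINC: 62238-1 If not available, derive from creat". A stored value comes first, with no limit on its age.
- **Systolic pressure.** "Take last value in PHKG ; SBP= LOINC: 8480-6", and in the same row "average value across a period of time".

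The physician's task is described only as "collect + analyse + enter data into a standalone web page calculator". The function printed in Section 10.6 takes "hdlCholesterol, totalCholesterol, creatinin, crp, hrFutureEvent = 1, usingAnticoag, region" among its arguments. It uses CRP as entered and always derives eGFR from creatinine.

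CVD Metric 2 defines accuracy as the percentage difference in the score output. Section 9.2 takes it against both the treating and the senior physician, and Section 9.1 sets a target of 80% or more. Where scores differ, the senior physician inspects AIDAVA's parameters and picks one of three reasons: incomplete record, AIDAVA error, or physician error.

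**The concern.** The endpoint compares final scores, so it mixes two things: whether AIDAVA pulled the right data from the record, and whether the two scorers chose the same value when several were available. Only the first says anything about curation. If the physician enters the latest CRP while AIDAVA correctly applies its rule and uses an older value or the default, the gap is charged to AIDAVA.

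The mix could also differ between generations. Visit 1 may fall in an "inpatient stay during index MI event", whereas returning patients attend G2 as outpatients 16 to 18 months later. Section 9.3 plans a paired comparison of accuracy between G1 and G2. A change in how often the input rules bite would appear there as a change in the tool.

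Form 14 (the CVD specialist form in Section 10.3.4) records the physician's score and time but none of the values entered. The two sources of difference therefore cannot be separated from that form afterwards.

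**Working it through.** The protocol gives no figure of its own on this point, so there is nothing to reproduce. The check is a sensitivity calculation with the Section 10.6 function.

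**Inputs from Section 10.6.** CRP enters as 0.1517601731 × ln(CRP), systolic pressure as 0.0018913154 per mmHg, and eGFR as −0.0396752081 × eGFR + 0.0002186126 × eGFR². Risk = 1 − (1 − 0.1658228)^exp(LP + 0.0463729 − ln(region ratio)).

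**Assumptions.** Region ratio 1; CRP and its limit of 15 in mg/L; accuracy = smaller risk divided by larger risk, per patient. The illustrative patient is a man of 65 with coronary disease, non-smoker, no diabetes, 0 years since first diagnosis, systolic pressure 135, cholesterol 4.9 and HDL 1.2 mmol/L, creatinine 92 µmol/L (derived eGFR 76.1), on antithrombotic treatment.

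**Starting point.** At CRP 2.2, LP = −0.2439 and risk = 1 − 0.8341772^exp(−0.1975) = 13.8%.

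**CRP, AIDAVA on the default of 2.2**
- Physician enters 16: change in LP = 0.15176 × ln(16/2.2) = 0.301; physician risk 18.2%; agreement 13.8/18.2 = 76%.
- Physician enters 40: change 0.440; risk 20.6%; agreement 67%.

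**CRP, AIDAVA rolled back to an earlier 10** (AIDAVA risk 17.1%)
- Physician enters 16: change 0.071; agreement 94%.
- Physician enters 40: change 0.210; agreement 83%.

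**Does this depend on the patient?** Varying AIDAVA's own risk from 10% to 40%, default against 16 gives 75% to 80%, default against 50 gives 64% to 71%, and rollback to 10 against 50 gives 79% to 83%. Agreement falls to exactly 80% at a CRP ratio of 4.8 (risk 10%) to 7.5 (risk 40%). Against the default that is an entered CRP of about 10.5 to 16.4. Since the rule acts only above 15, nearly every case that ends on the default would be under 80% if the physician enters the last value.

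**eGFR**
- Stored 70 against derived 60: change = −0.0396752 × 10 + 0.0002186 × (4900 − 3600) = −0.113; risks 14.4% and 16.0%; agreement 90%.
- Stored 85 against derived 55: agreement 78%, but this needs a 30-unit gap.

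**Systolic pressure**
- 110 against 135: change = 0.0018913 × 25 = 0.047; risks 13.2% and 13.8%; agreement 96%.

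**If both scores use the same rules**, the rule-driven difference is zero, and what remains is extraction or physician error.

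**The case against.** **The physician may apply the same rules.** The table is introduced as the specification for computing the score, and the text after it says both AIDAVA and the physician compute that score. A reader might infer that the physician departs from the rules. The protocol does not say so; it is silent on which values are entered. The point is only that nothing requires the physician to follow them.

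**There is a senior review.** This is a real safeguard. The senior physician sees each parameter with its source and transformation, and Section 9.2 adds a second accuracy against the senior's score. A rollback would therefore be visible, and some cases could be filed as physician error. But none of the three reasons clearly fits two correct readings under different rules, and no passage says accuracy is recomputed after review.

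**Agreement with expert practice may be what is wanted.** Metric 2 is worded as a comparison with an expert-entered score, so input choice can legitimately belong to it. This is a good reason to keep the raw figure. It does not help interpret a shortfall whose cause was not recorded.

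**The tool need not fail the 80% target.** A reader might infer that it will. The documents do not support that. The formula behind 80% is undefined; if it is a mean or a share over patients, the result depends on how many are affected, which is not given. Rollback to 10 stays above 80% at CRP 16 and 40. Whether the web calculator accepts such CRP values, or asks for eGFR, is also not in the documents.

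**Imposing rules on the physician has a price.** It would alter the task timed as TCVD and make the reference less independent. This stands and shapes the fix.

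**Conclusion.** The concern holds in this form: the input rules are written for AIDAVA, the reference score is not bound by them, and an output-only accuracy cannot tell a different input rule from an extraction error. The three inputs are not equally important. CRP alone can move agreement below 80% at plausible settings of the calculation, mainly when AIDAVA falls back on the default (about 76% to 67% for an entered 16 to 40). A modest eGFR difference costs about 10 points and the systolic difference about 4. The systolic row still needs settling because it states two rules.

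These sizes rest on the assumed mg/L unit, region ratio 1 and a per-patient ratio of risks. They are conditional on the physician entering the last recorded value. Minor to moderate: accuracy here is a secondary endpoint in a proof-of-concept study whose outputs are not used for clinical decisions.

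**What to change.** 1. In Section 3.2.2, reconcile the eGFR row with the Section 10.6 function, keep one systolic-pressure wording, and give the unit of the CRP limit.
2. Add to Form 14 the CRP, creatinine or eGFR, and systolic values the physician entered, each with its date.
3. Keep ACVD as defined. Beside it, report an accuracy in which the physician's score is recomputed under AIDAVA's input rules. The difference between the two figures is the part due to input convention.
4. Add a fourth discrepancy reason to Section 3.2.2: different input rule, both readings correct.

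The cost is a short text change and a few more entry fields per CVD patient. The fields should be completed outside the timed TCVD task so that the time endpoint is not altered. The physician's choice of values stays free, so the reference keeps its independence.

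### SMART specification table: the coded antithrombotic rule disagrees with its own examples on a DOAC taken alone, and the diabetes default uses a coefficient that is not in the formula

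*Protocol*

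**What the plan says.** The table in Protocol Section 3.2.2 tells AIDAVA how to derive each SMART input from coded data and what to use when the input is missing.

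- **Antithrombotic row, coded rule.** The flag is Y for "one or more drugs of category Platelet aggregation inhibitors excl. Heparin (ATC = B01AC) OR A combination of" the same category together with "one or more drug of category Direct factor Xa inhibitors (ATC = B01AF").
- **Antithrombotic row, examples.** These include "Direct oral anticoagulants (DOAC") and, as a further entry, "Ascal / Aspirin + low dose direct working oral anticoagulation (DOAC").
- **Antithrombotic row, missing value.** The flag is Y. No condition for N is written.
- **Antithrombotic row, coefficient.** The term "0.2107210313 * usingAnticoag" is printed with a plus sign in 3.2.2. The code in Section 10.6 subtracts it.
- **Diabetes row.** The term is "0.3181706587 [if diabetic"], and the 10.6 code uses the same number: "0.3181706587 * diabetesDiagnosis". The missing-value cell reads "VAL = 17% * 0.223 (average").

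CVD secondary Metric 2 compares AIDAVA's score with the score a physician obtains from the U-Prevent web calculator, as a percentage difference in output. Section 9.1 hypothesises an accuracy of 80% or more and does not define that measure further.

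**The concern.** A programmer following the coded rule and a reader following the examples give different flags to the same patient. The treating physician does not work from this table but enters data into a web page, so a gap in an input rule appears as disagreement between AIDAVA and the physician even when AIDAVA has curated the record perfectly.

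Section 3.2.2 gives the senior physician three reasons for a discrepancy: incomplete record, AIDAVA error, physician error. None covers a fault in the specification, so such a case would be attributed to the wrong cause. The diabetes default raises the same issue on a smaller scale: a constant in the missing-value column does not match the formula it feeds.

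**Working it through.** **1. Antithrombotic rule as logic.** Let A be a B01AC drug on record and B a direct oral anticoagulant (B01AF in the rule). The rule is A OR (A AND B), which equals A.

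| A | B | Coded rule | Examples |
|---|---|---|---|
| no | no | N | N |
| no | yes | **N** | **Y** |
| yes | no | Y | Y |
| yes | yes | Y | Y |

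Rule and examples disagree in one cell of four: the anticoagulant without an antiplatelet. The first row takes an absent code to mean N. If it is instead read as missing, the default makes that cell Y, and the row does not say which reading applies.

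**2. Diabetes default.**
- As printed: 0.17 × 0.223 = 0.0379.
- With the row's coefficient: 0.17 × 0.3181706587 = 0.0541.
- Ratio 0.0379 / 0.0541 = 0.70; gap in the linear predictor 0.0162; hazard factor exp(0.0162) = 1.016.

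None of the 17 coefficients in the formula rounds to 0.223; the nearest is 0.2244665798, for peripheral artery disease. If the printed value were an input to be multiplied by the coefficient again, the contribution would be 0.0379 × 0.318 = 0.0121, which does not match either.

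**3. Effect on the score.** The 10.6 code gives risk = 1 − (1 − 0.1658228)^exp(LP + 0.0463729 − log(region ratio)).

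- Assumed: man aged 60, systolic pressure 140, coronary disease = 1, non-smoker, no other vascular disease, region ratio 1.
- From the table's missing-value column: 1 year since diagnosis, total cholesterol 4.9, HDL 1.2, creatinine 92, and CRP entered as 2.2.

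eGFR = 32788 × 92^(−1.154) × 60^(−0.203) = 77.4. Without diabetes and with flag N, LP = −0.1549.

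| Case | LP | Ten-year risk |
|---|---|---|
| Flag N | −0.1549 | 15.01% |
| Flag Y, minus sign (10.6) | −0.1549 − 0.2107 = −0.3656 | 12.34% |
| Flag Y, plus sign (3.2.2) | −0.1549 + 0.2107 = 0.0558 | 18.2% |
| Flag Y, minus sign, diabetes default as printed | −0.3656 + 0.0379 = −0.3277 | 12.79% |
| Flag Y, minus sign, diabetes default with row's coefficient | −0.3656 + 0.0541 = −0.3116 | 12.98% |

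- Minus sign: N against Y is 15.01 / 12.34 − 1 = +22%; Y against N is 12.34 / 15.01 − 1 = −18%.
- Plus sign: N against Y is 15.01 / 18.2 − 1, about −17%.
- Diabetes: 12.98 / 12.79 − 1 = 1.5%.

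**4. Dependence on the profile.** Take any risk r under N and apply 1 − (1 − r)^exp(±0.2107). For r from 10% to 40%, switching to Y changes risk by +22% to +17% with the plus sign, or −18% to −15% with the minus sign. For the same values of r, the diabetes gap changes risk by 1.6% down to 1.2%.

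**The case against.** The best reply is that this is one ambiguous cell and one small constant in a secondary score that is not used for care. Much of that is right.

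- **A drug class left out.** A reader might infer that factor Xa inhibitors are absent from the rule. They are named, but only together with B01AC. What the rule misses is that class taken alone.
- **The default of Y as a contradiction.** Presence meaning Y and absence implying N is the pattern of several rows, and the last column is meant for missing data. The default is therefore not wrong in itself. It leaves open whether an absent code means not taking or not recorded. That the flag would always be Y follows only if every absent code counts as missing, which the table does not say.
- **Lost layout.** Bullets in the example cell did not survive text extraction. The stand-alone reading rests on the separate entry for aspirin plus a low-dose anticoagulant. That supports it well but is not proof.
- **A 20% tolerance used up by one flag.** This inference is tempting beside the 80% target, but the protocol sets no per-patient tolerance, and most of the relative changes above are below 20% anyway.
- **A profile on table defaults.** Systolic pressure has no default and the coronary disease default is N, so 140 and 1 are assumptions made here.
- **Senior review.** A senior physician sees every parameter when scores differ, so a wrong flag could be noticed. It still could not be recorded as a specification fault.

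After these concessions, the mismatch between rule and examples remains, as does the 0.223 that matches no coefficient.

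**Conclusion.** Both defects hold. Followed as written, the coded rule gives N to a patient on a direct oral anticoagulant alone, against the row's own examples, and the diabetes default is 70% of what the row's coefficient implies.

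For an affected patient the flag is worth about 15 to 22% of the score in relative terms, over baseline risks of 10% to 40%. Those affected are patients on such a drug alone or without medication data. Their number is not given and is probably small. The diabetes default is worth 1 to 2% and applies only when status is missing.

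The direction of the antithrombotic error depends on which printed sign is used: with the 10.6 minus sign the coded rule overstates risk relative to the examples, and with the 3.2.2 plus sign it understates it. The documents do not show how the web calculator defines this input, so nothing here says which drug rule is right. The severity is minor: worth correcting because it is cheap, but no threat to the primary comparison.

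**What to change.** 1. Reconcile the coded antithrombotic rule with its own examples, so that AIDAVA and the physicians code the input the same way.
2. State that N applies when a medication list is present without a qualifying drug, and that the default of Y applies only when no medication list exists.
3. Replace 0.223 in the diabetes default with 0.3181706587, and say that the product is the contribution to the linear predictor.
4. At the same time, reconcile the sign of the antithrombotic coefficient between Sections 3.2.2 and 10.6.

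The cost is a few table cells and a unit test that covers the four drug combinations, an absent medication list and missing diabetes status. No new data collection is needed.

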The senior physician will then be able to decide on one of the following reasons for discrepancy. Health record incomplete: the information was not available in the medical record, while it should have been – and therefore AIDAVA could not identify the right value.

- Error in AIDAVA: the information is rightly included in the medical record, but AIDAVA did not include this information properly
- Error from physician: AIDAVA is right and the junior physician evaluation is not correct.

To assess the longitudinal aspects of AIDAVA, the SMART score will be calculated 2 times (after G1 and \pm 16 to 18 months later, at the end of G2 use year follow-up). The aim is to see if modifiable risk factors can be captured and risk can be calculated by AIDAVA automatically and reliably.

4. Study Design

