SDPO	GO	With ± 15 patients on site	 EBCx: estimated total effort (person min, person hours or person days) for BC specialist and supporting local team to answer the queries (BC1, BC2, BC3 described in Section 3.2.1) across sites TBCx: estimated duration (min, hours or days) for the BC specialist to have an answer to the queries (BC1, BC2, BC3) across sites. Duration = time between the first request and the time the answer is provider 		
SDP1	G1	All patients	 EBCx: total effort for BC specialist (and local team) to answer the queries (BC1, BC2, BC3) across sites TBCx: duration (min, hours or days) for the BC specialist to have an answer to the queries (BC1, BC2, BC3) across sites. HBCx: answer to the query as provided by human BC specialist ABCx: answer to the query as computed by AIDAVA ACCx: accuracy of calculation by AIDAVA compared to BC specialist 		
SDP2	G2		Same than SDP1 - for G2		
		1	CVD		
SDP1	G1	All patients	 CVD. SMART risk score computed by AIDAVA TCVD1.1/TCVD1.2. Time required for the treating/ senior physician to compute the SMART score (collect + analyse + enter data into a standalone web page calculator) CVD1.1/CVD1.2. SMART score computed by treating / senior physician ACVD1.1/ACVD1.2. Accuracy of automatic calculation of the score compared to treating/senior physician-entered score 		
SDP2	G2		Same than SDP1 - for G2		

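### The physician SMART scores used to judge AIDAVA's accuracy, above all the senior physician's, need not be fixed before AIDAVA's output is seen, so their independence is not assured

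*Protocol*

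**What the plan says.** **Order of scoring (Protocol 3.2.2).** "The score will be computed by AIDAVA and by the treating (junior) physician". Next, "It will then be checked by the senior physician; in case of discrepancy between the score computed by AIDAVA and by the physicians", the senior asks how AIDAVA reached its values and decides the reason. For this, "The senior physicians will be presented with a table with all the parameters used to compute the score", and can trace each value to its source and transformation. One of the three reasons on offer is "Error from physician: AIDAVA is right and the junior physician evaluation is not correct".

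**References for accuracy.** The endpoint table in 3.2.2 compares AIDAVA with the treating physician's score only, as a percentage difference. Section 9.2 adds the senior score: "ACVD1.1/ACVD1.2. Accuracy of automatic calculation of the score compared to treating/senior physician-entered score". It also lists "TCVD1.1/TCVD1.2. Time required for the treating/ senior physician to compute the SMART score".

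**Criterion.** Section 9.1 sets an accuracy of 80% or more for G1 and does not say which reference it uses.

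**Visits.** Section 4.4.2 has at Week 1 Day 5 "First calculation of SMART risk score by AIDAVA (automatically) and CVD expert (manually", and a second calculation by both at Week 2 Day 5.

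**Sight of AIDAVA's score.** Section 8 says physicians calculate manually and may compare with AIDAVA's result. The Week 1 Day 5 monitoring form for CVD patients (10.3.2) records whether CVD specialists viewed the system's score.

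**Entry form.** The CVD specialist form (Form 14, 10.3.4) has a specialist's score, another person's score and a single time field. It has no lock, no order of entry, and no record of whether AIDAVA's output had been seen.

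**The concern.** An accuracy study needs a reference formed without knowledge of the result under test. If the senior physician can settle on a score with AIDAVA's inputs and reasoning in view, the reference may absorb AIDAVA's value, and agreement rises without any better scoring.

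A second route is the trigger for explanations. They are sought only when scores differ. If AIDAVA and the junior physician make the same mistake, for example from the same gap in the record, they agree and nothing prompts a request for explanation.

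At stake is the secondary CVD hypothesis of 80% accuracy. The analysis cannot repair this later, because a physician who has seen AIDAVA's output cannot be made blind to it.

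**Working it through.** **Step 1. Is the senior score a reference?** Yes, through CVD1.2 and ACVD1.2 in section 9.2. It stands beside the treating physician's score and does not replace it.

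**Step 2. Is it fixed before AIDAVA's output is seen?** Section 3.2.2 describes a check made after AIDAVA and the junior have scored, with AIDAVA's parameters available. Section 9.2 describes a score that the senior computes and that is timed. The protocol does not say whether that calculation precedes or follows the check, and Form 14 does not settle it.

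**Step 3. Is the treating physician's score protected?** At Week 1 Day 5 no order is stated. The same day's form anticipates that specialists view AIDAVA's score. The Week 2 Day 5 calculation for the same patient comes after that. The schedule of activities puts the CVD data user form at Week 2 Day 5, while 4.4.2 also lists it in Week 1, so the score that feeds ACVD1.1 may be an exposed one.

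**Step 4. Direction and possible size.** The protocol gives no figure to reproduce. The following illustration treats agreement as yes or no, although 3.2.2 defines accuracy as a percentage difference. It supposes that the reference is a senior score settled after review, with only discordant scores revisited. Assumed inputs:
- pA: true accuracy of AIDAVA
- eP = 0.10: junior error rate when AIDAVA is right
- c: chance that the junior shares AIDAVA's error
- a: chance that the senior adopts AIDAVA's wrong value
- b: chance that the senior wrongly sides with the junior

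Agreement with the junior = pA(1 − eP) + (1 − pA)c.

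Agreement with the post-review senior = pA(1 − eP·b) + (1 − pA)c + (1 − pA)(1 − c)a.

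The 45 CVD patients are 3 × 15 (section 9.4), and 80% of 45 is 36. Results at pA = 0.70:

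| c | a | b | vs junior | vs post-review senior | chance of at least 36/45 (senior) |
|---|---|---|---|---|---|
| 0 | 0 | 0 | 0.630 | 0.700 | 0.093 |
| 0 | 0 | 0.3 | 0.630 | 0.679 | 0.053 |
| 0 | 0.2 | 0 | 0.630 | 0.760 | 0.334 |
| 0.2 | 0 | 0 | 0.690 | 0.760 | 0.334 |
| 0.2 | 0.2 | 0.3 | 0.690 | 0.787 | 0.502 |
| 0.2 | 0.2 | 0 | 0.690 | 0.808 | 0.641 |

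Last row: 0.70 + 0.30 × 0.2 + 0.30 × 0.8 × 0.2 = 0.70 + 0.06 + 0.048 = 0.808. Second row: 0.70 × (1 − 0.10 × 0.3) = 0.679.

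An independent, error-free reference would show 0.700, with a chance of 0.093. At pA = 0.75 the same grid gives 0.728 to 0.840, and a chance of 0.178 to 0.827 against 0.280.

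Under this supposition concordant pairs stay concordant and discordant pairs can only stay or move to agreement, so ACVD1.2 cannot fall below ACVD1.1. Against the truth the bias can be upward, nil or slightly downward.

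**The case against.** A reader might infer that the senior score **is** formed after seeing AIDAVA's result. The documents do not establish that. Section 9.2 times the senior's own work of collecting, analysing and entering data, and 3.2.2 speaks of a discrepancy with the physicians in the plural, which fits a senior score that already exists. This stands. The defect is that the order is left open.

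A reader might also infer that only discrepant cases are checked. The senior check in 3.2.2 carries no condition; the discrepancy governs the request for explanations. The review yields a reason, and nothing says that a score is revised. This also stands, and it narrows the shared-error point to cases that may go unexamined.

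It is tempting, too, to say that a true failure of the 80% criterion would read as a pass. With 70% true agreement and a senior who moves to AIDAVA's value in 25%, 50% or 75% of disagreements, 1 − 0.30 × (1 − share moved) gives 77.5%, 85% or 92.5%. Those shares are assumptions, and the sum counts every move as false agreement although 3.2.2 allows that AIDAVA may be right. It further assumes that ACVD1.2 decides the criterion, which no passage says.

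Finally, this is a secondary endpoint in a proof-of-concept study, the G1 CVD analysis is descriptive, and the score may not guide care. That limits the weight of the point. It does not justify leaving open a sequence that cannot be recovered afterwards.

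**Conclusion.** The point holds in a limited form. The protocol names the senior score as a reference for AIDAVA's accuracy, gives the senior access to AIDAVA's parameters and derivations, allows specialists to see AIDAVA's score, and nowhere requires a physician score to be fixed first. ACVD1.2, and possibly ACVD1.1 at Week 2, is not assured to be independent.

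Inflation is likely, not certain, and the protocol does not allow its size to be derived. The illustrated 0.68 to 0.81 at a true 0.70 rests on assumed rates, yes/no agreement, and a reference settled after review. The discrepancy review does not alter the treating-physician comparison defined in 3.2.2; for that comparison the gap is only that exposure before scoring is not ruled out. The change is worth making before data collection, in proportion to a secondary endpoint.

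**What to change.** In section 3.2.2 and Form 14:
- The treating and senior physicians each enter and lock their own inputs, score and time for every CVD patient before any AIDAVA score or parameter table for that patient is shown. Add a time field for the senior physician, since TCVD1.2 has none.
- Take the accuracy comparison from scores locked before first exposure, and flag later ones, such as an exposed Week 2 recalculation, as exposed.
- Compute ACVD1.1 and ACVD1.2 from the locked values, and state in 9.1 which of them the 80% criterion uses.
- Keep the discrepancy review only to classify reasons.

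**Cost.** A change of sequence, a lock and one extra field. Section 9.2 already calls for the senior score and time. Measured accuracy may be lower. A locked senior score for every patient can reveal some errors shared by AIDAVA and the junior, but one drawn from the same incomplete record will not remove them all.
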